6.5.2 Secondary outcomes

The proposed secondary outcomes in a future large scale trial will be the difference in measures of quality of life, anxiety and depression, and fatigue between the intervention and usual care (control) group. Data will be collected in the proposed rehearsal feasibility study and pilot trial.

Quality of life: EQ-5D, which is a parsimonious measure of health-related quality of life consisting of five dimensions: mobility, self care, usual activities, pain/discomfort, anxiety/depression, will be used to measure quality of life [13]. A recent review shows a substantial and growing body of literature using the EQ-5D in cancer, and draws the conclusion that it is a valid and reliable instrument [14]. For our pilot work, SF-36 will also be used to measure quality of life [60]. Both EQ-5D and SF-36 are used in health economics as a variable in the quality adjusted life year calculation to determine the cost-effectiveness of an intervention. SF-36 comprises eight dimensions: vitality, physical functioning, bodily pain, general health perceptions, physical role functioning, emotional role functioning, social role functioning, mental health.

Anxiety and depression: The Hospital Anxiety and Depression Scale (HADS), which consists of 14 questions, 7 for anxiety and 7 for depression, will be used to measure anxiety and depression [17]. A meta-analysis suggests that it is sufficiently sensitive for identifying depression and anxiety in patients with cancer [18].

Fatigue: The Functional Assessment of Cancer Therapy Fatigue (FACT-F) [52], which is a 13-item fatigue FACT subscale, will be used to measure cancer-related fatigue. A recent systematic review of the scales used for the measurement of cancer-related fatigue show that there is no accepted definition of cancer-related fatigue and no agreement on how it should be measured [15]. Nevertheless, the review recommends the use of FACT-F. Moreover, an evaluation of a 12 week resistance exercise programme in patients with prostate cancer used FACT- F and found benefits from resistance training on cancer-related fatigue, suggesting the instrument is sensitive [16].

6.5.3 Process variables

Self-efficacy and *risk perception* will be measured to assess if these psychological constructs predict attendance at cardiac rehabilitation classes and changes in health outcomes arising from the intervention.

- General self-efficacy, which is the belief that one can perform difficult tasks or cope with adversity, will be measured using a ten-item scale [61]. Physical exercise self-efficacy, which is the belief that one can engage in, and meet physical activity goals, will also be measured [62].
- According to the behaviour motivation hypothesis [66], perceived risk is positively and directly related to health behaviour. Risk perception of suffering from diseases has been found to play an important role in the development of intentions to perform physical activity among older adults [63] and in explaining cancer-related behaviours [64;65]. Given the lack of agreement about quality of methods of measuring cancer risk perception, we will include absolute (i.e. estimation of personal risk) and comparative measures (i.e. comparison of personal risk to other people's risk). We will also include conditional (i.e. rating the probability that a certain event (e.g. cancer recurrence) will occur given their the adaptive behaviour (e.g. increasing physical activity) is, or is not, performed) and unconditional (i.e. rating the probability that a certain event will occur without specifying the adaptive behaviour) measures [67].

6.5.4 Clinical variables

In addition, clinical confounding factors will be assessed:

- Colon or rectal surgery;
- Surgical intervention (e.g. laparoscopic or open surgery);
- Temporary (a loop ileostomy) or permanent stoma or no stoma;
- Chemotherapy or no chemotherapy.

6.6 Data collection for Feasibility study (Phase 1)

The purpose of the feasibility study is to evaluate and refine the intervention and main components of the trial. To meet Phase 1 study objectives we will carry out the following: cardiac rehabilitation physiotherapists will firstly attend a one-day training course delivered by a cancer-exercise specialist and complete an evaluation form about the

training. Then in one research site (Stirling), 12 cancer patients will be screened, recruited and referred for rehabilitation. The proposed outcomes and processes will be measured using the instruments we aim to use in a larger scale trial. Patients will be allocated to the next available rehabilitation class, which means that all 12 cancer patients are unlikely to attend the same classes. Patients will then attend a 10 week rehabilitation programme in a cardiac rehabilitation setting. A screening and recruitment log will be completed by a researcher to document all patients considered for the study and subsequently included or excluded at each stage of the recruitment process and reasons given. This will include information such as; when the patient was given information about the study, referred to cardiac rehabilitation, attended for clinical/risk assessment, and received an offer to attend rehabilitation classes. A researcher will also complete an intervention record log to document the number of classes attended by participants, type and duration of exercises, and which education classes the patient attended. On completion of rehabilitation, semi-structured face-to-face interviews will be conducted with, i) 12 cancer patients and a nominated family member, ii) 6 cancer and 6 cardiac clinicians who were involved in screening, recruitment, referral and/or delivering the intervention, and iii) 6 cardiac patients involved in the mixed cancer/cardiac patient rehabilitation classes, in order to gather responses about the acceptability of the intervention and trial procedures. Further description about data collection for Phase 1 is provided below.

6.6.1 Training

Training and on-going support is essential to promoting of intervention fidelity [53]. Cardiac physiotherapists delivering the intervention (i.e. who deliver exercise classes in a cardiac rehabilitation setting to mixed classes of cardiac/cancer patients) will attend a one-day introductory course on cancer and exercise delivered by [name], Director of Canrehab (www.canrehab.co.uk). The introductory course gives an overview of cancer types, treatments, medications and side effects. It describes the evidence-based benefits of physical activity in this population group and provides the current guidelines to physical activity and exercise management and prescription during and after treatment for cancer. A session on behaviour changes theories and practices to enhance engagement in behaviour change will also be incorporated as part of the cancer and exercise training. To meet Objective 3, those attending the training will complete an evaluation sheet about the training and will also be asked questions about the training and support in a semi-structured face-to-face interview (see Section 6.6.6).

6.6.2 Screening and recruitment of cancer patients

- 1. Potential recruits will be identified from existing patients at follow up. All colorectal cancer patients who have completed surgery will be screened by a colorectal cancer Clinical Nurse Specialist at the first follow up appointment following surgery (approximately 6 weeks from date of surgery) to assess if it is safe for them to engage in physical activity from a cancer clinical perspective. The clinician will assess if there are contraindications to exercise due to cancer and late effects of treatment (e.g. patients with severe anaemia or with compromised immune function). At the follow up clinic, the nurse will give eligible patients an information sheet about the study and talk them through it. If the patient agrees to participate the nurse will refer the patient to cardiac rehabilitation by email, fax or letter and advise the patient that the cardiac rehabilitation service will contact them. Patients who decline to participate having read the study information will be asked if they would be willing to complete a questionnaire about reasons for declining to participate.
- 2. A member of the cardiac multi-disciplinary team (e.g. cardiac physiotherapist or nurse) will contact cancer patients and invite them to attend a cardiac rehabilitation clinical /risk stratification assessment to determine whether the patient will be able to safely exercise from a cardiac clinical perspective and plan physical activity goals tailored to individual patient needs. Patients who are deemed safe to exercise will be invited to attend cardiac rehabilitation classes. Patients who decline to attend a clinical /risk stratification assessment will be asked if they would be willing to complete a questionnaire about reasons for declining to participate.
- 3. A researcher will contact patients who have agreed to participate and have been assessed and arrange a time for them to formally consent in writing to participate in the study and then if they have consented, have proposed outcomes measured. Consenting will be within five days of the patient being offered a place to attend the cardiac rehabilitation classes. Consenting will be carried out either in the patient's own home or at the cardiac rehabilitation facility. The researcher will confirm eligibility and consent patients to the study. If consent is declined, patients will be asked if they would be willing to complete a questionnaire concerning their reasons for non-participation.

To meet Objective 4, a screening and recruitment log will be completed by a researcher to document all patients considered for the study and subsequently included or excluded at each stage of the recruitment process and reasons given. This will also include information such as; when the patient was given information about the study, referred to cardiac rehabilitation, attended for clinical/risk assessment, received an offer to attend rehabilitation classes.

6.6.3 Intervention

All recruited cancer patients will attend post-hospital rehabilitation in a cardiac rehabilitation setting (see section 6.4 for more detail). To meet Objective 1, a researcher will contact participants each week by telephone and complete an

intervention record log to document for example, type and duration of exercises completed and content of education sessions attended.

6.6.4 Interviews with cancer patients and nominated family member

To meet Objectives 1, 2 and 4, at the end of the intervention, face-to-face semi-structured interviews [54] will be conducted with the cancer patients about the acceptability of the intervention, screening and recruitment processes and study instruments. Patients will also be consulted about what outcomes from rehabilitation are most important to them, which will inform our final choice of outcomes in the pilot trial (Phase 2) as well as in a future more definitive trial of the intervention. Patients will be invited to nominate a family member who will be interviewed separately about the intervention and ways in which they might be involved in a rehabilitation programme in the future. The interviews will last approximately 45 minutes, be audio-recorded and will take place at the hospital or cardiac rehabilitation facility. Only those who give written consent to participate in the study will be interviewed by a researcher. All researchers involved in conducting interviews will be receive guidance and support by applicants ([name] and [name]) who are very experienced in conducting qualitative research and have expertise in conducting interviews with patients with cancer in a sensitive manner using good communication skills (e.g. showing empathy, interpreting body language).

6.6.5 Recruitment and interviews with cardiac patients

All cardiac patients will be informed that the study is taking place at the cardiac rehabilitation facility and that the classes that they attend may include cancer patients. To meet Objectives 1 and 2, at the end of the intervention 6 cardiac patients who attended rehabilitation classes at the same time as cancer patients will be approached by a researcher and invited to attend a semi-structured face-to-face interview [54] about their experiences of having cancer patients participate in rehabilitation. The interview will last approximately 45 minutes, be audio-recorded and will take place at the hospital or cardiac rehabilitation facility. Patients will be purposively sampled so that the study includes responses from younger and older men and women. Only those who give written consent to participate in the study will be interviewed by a researcher.

6.6.6 Recruitment and interviews with clinicians

To meet Objectives 1, 2 and 4, cancer and cardiac clinicians involved in screening and recruitment and/or delivering the intervention will be approached by a researcher and invited to attend a semi-structured face-to-face interview [54] about their experiences of the trial procedures and the intervention. The interview will last approximately 45 minutes, be audio-recorded and will take place at the hospital or cardiac rehabilitation facility. Only those who give written consent to participate in the study will be interviewed.

6.7 Data collection for pilot RCT (Phase 2)

The purpose of the pilot RCT with a process evaluation is to assess whether trial components and procedures work in practice and generate date to inform the sample size calculation for a larger scale trial of the planned intervention. To meet Phase 2 study objectives we will carry out the following: In three sites, cancer patients will be screened, recruited, have proposed outcomes measured (i.e. instruments we aim to use to measure effect in a larger scale trial) and then randomised to the intervention or control group. Those randomised to the intervention group will be referred for rehabilitation and attend rehabilitation classes in a cardiac rehabilitation setting and those randomised to the control group will receive 'Staying healthy after bowel cancer' booklet by Bowel Cancer UK, which includes a section on Staying Fit. A screening and recruitment log will be completed by a researcher to document all patients considered for the study and subsequently included or excluded at each stage of the recruitment process and reasons given. A researcher will also complete an intervention record log to assess intervention fidelity. On completion of rehabilitation, semi-structured face-to-face interviews will be conducted with 24 cancer patients with equal split between research sites and each trial to gather responses about the acceptability and the intervention and trial procedures. Twelve clinicians involved in recruitment and/or delivering the intervention split between the research sites will also be interviewed. Further description about data collection for Phase 2 is provided below.

6.7.2 Screening and recruitment of cancer patients

Screening and recruitment of cancer patients by clinicians for the pilot trial will follow the same procedures as outlined for the feasibility study (Phase 1), which are described in Section 6.6.2 above. However, we may make slight modifications to screening and recruitment procedures based on the findings of the feasibility study and these will be documented. To meet Objectives 5 and 10, a screening and recruitment log will be completed by a researcher to document all patients considered for the study and subsequently included or excluded at each stage of the recruitment process and reasons given. This will also include information such as, when the patient was given information about the study, referred to cardiac rehabilitation, attended for clinical/risk assessment, and received an offer to attend rehabilitation classes.

6.7.3 Randomisation

Patients will be randomised to the intervention or control group after they have consented to participating in the study and after baseline primary and secondary measures have been collected. Randomisation with stratification by centre will be conducted by Tayside Clinical Trials Unit.

6.7.4 Intervention and control

Participants will either receive rehabilitation (intervention group) or a 'Staying healthy after bowel cancer' booklet by Bowel Cancer UK (control group), as described in Section 6.4 above. However, we may make slight modifications to the intervention based on the findings of the feasibility study, which will be documented. To optimise intervention fidelity [53], interventionists will be expected to follow the cancer patient rehabilitation pathway (see Appendix 1) for this study and their site-specific rehabilitation programme. To meet Objectives 6 and 9, a researcher will contact participants randomised to the rehabilitation group each week by telephone in order to complete an intervention record log to document for example, type and duration of exercises completed and content of educational classes attended for participants receiving the intervention. A researcher will also contact participants randomised to the control group to record for example, any advice given about exercising.

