The exercise class will be followed by 30/60 minutes (depending on research site) of education (e.g. stress management, diet, drug therapy, smoking cessation, benefits of exercise and relaxation). A member of the cardiac multi-disciplinary team will deliver some educational sessions to a mixed class of cancer/cardiac patients because they are relevant to both cancer and cardiac patients (e.g. smoking cessation, relaxation). A colorectal cancer nurse will deliver some educational sessions (e.g. cancer therapies) to cancer patients. These educational sessions will either be delivered to a group of cancer patients (e.g. when cardiac patients receive a session about drug therapy from a member of the cardiac multi-disciplinary team, cancer patients will receive an equivalent session about drug therapy from a cancer nurse) or one-to-one by telephone (depending on research site). To optimise intervention fidelity, interventionists will be expected to follow the cancer patient rehabilitation pathway (Appendix 1) for this study, and also their site-specific rehabilitation programme. Patients randomised to the control arm of the pilot RCT (Phase 2 of the study) will receive 'Staying healthy after bowel cancer' booklet by Bowel Cancer UK, which includes a section on 'staying fit'.

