10.2 Risks to participants

This is a low risk study and major risks and safety issues are not anticipated. No invasive procedures are being used in this study. The intervention includes an exercise component during the period of recovery following surgery. Moderate physical activity is recommended for colorectal cancer patients during treatment and has no contraindications for most [49]. The American College of Sports Medicine recommend that cancer patients avoid inactivity and return to normal activity as soon as possible after diagnosis and treatment and should engage in at least 150 minutes per week of moderate intensity or 75 minutes per week of vigorous intensity aerobic physical activity, or an equivalent combination of moderate and vigorous intensity aerobic physical activity [59]. Evidence suggests that it is not only feasible to exercise during the period of recovery post-surgery but that it can improve cardiovascular fitness, muscle strength, body composition, fatigue, anxiety, depression, self-esteem, and quality of life [49]. Nevertheless, effects of treatment may increase the risk of exercise-related injuries and adverse effects and so during the screening process for study participation those patients who are contraindicated for moderate intensity physical activity or who have an injury or illness which might be aggravated by exercise, will be excluded from the study:

- 1. The patient's cancer clinical team at a post-treatment follow up appointment will assess if there are contraindications to exercise due to cancer and late effects of treatment (e.g. patients with severe anaemia or with compromised immune function).
- 2. A cardiac rehabilitation clinician (e.g. cardiac nurse/cardiac physiotherapist) will conduct a clinical/risk stratification assessment to determine whether a patient can safely exercise from a cardiac clinical perspective.
- 3. During rehabilitation the cardiac physiotherapist running the exercise class will monitor patients for adverse events (e.g. chest pain, extreme breathlessness) and will decide whether it is safe for the patient to continue participation. An adverse events log will be kept for the duration of the study.
- 4. Patients will be advised and encouraged to contact their colorectal cancer Clinical Nurse Specialist if they have any questions or concerns about their health during the trial.

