Stage 4 Deliver rehabilitation programme. Date recorded and sent to Cancer CNS by email or letter. 1. Cardiac rehabilitation provider with additional input from cancer CNS/nurse consultant Stage 5 & 6 Conduct final rehabilitation assessment and discharge and ternsition to self management Attendance of rehabilitation classes and book patients onto rehabilitation programme. Date recorded and sent to Cancer CNS by email or letter. 1. Cancer patient attends rehabilitation classes. A record of when and which rehabilitation classes cancer patient attends recorded. 2. In accordance with standard cardiac rehabilitation service guidance, deliver other core components of rehabilitation (e.g. lifestyle, psychosocial status and quality of life, risk factor management, education, long-term management). 4. At end of the rehabilitation programme, refer cancer patient to colorectal CNS by email or letter. Date of referral recorded. Stage 5 & 6 Cancer Cinical Nurse Specialist (CNS)/nurse consultant 1. Contact cancer patient by email, phone or letter offering them a final assessment. Date of successful contact and proposed assessment date recorded. If after 3 attempts to contact patient has failed, or the patient declines offer of assessment a record of this is made. 2. Discuss and record patient achievements against original goals set out in the care plan (Stage 0). 3. Agree long-term self management plan based on individual patient goals and needs and encourage patient to take up opportunities to			

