## **Summary of Study Data**

All continuous variables will be summarised using the following descriptive statistics: n (non-missing sample size), number of missing records, mean, standard deviation, median, maximum and minimum. The frequency and percentages (based on the non-missing sample size) of observed levels will be reported for all categorical measures. In general, all data will be listed, sorted by subject and treatment and where appropriate by visit number within subject.

All summary tables will be structured with a column for each treatment in the order (Intervention, Control) and an additional column for the total population relevant to that table/treatment, including any missing observations'

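### Research contact about exercise, the contamination item and adverse event ascertainment are not specified alike in the two arms, although contamination and adverse events are to be reported between arms

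*Protocol*

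**What the plan says.** **Research contact.** Under protocol section 6.7.4, to serve Objectives 6 (contamination) and 9 (fidelity), "a researcher will contact participants randomised to the rehabilitation group each week by telephone in order to complete an intervention record log". The log covers "type and duration of exercises completed and content of educational classes attended for participants receiving the intervention". For the other arm the section says: "A researcher will also contact participants randomised to the control group to record for example, any advice given about exercising". It gives no frequency, mode or form for that contact. The Phase 2 timetable row for telephone calls refers to cancer patients generally, without arm or interval. Section 6.4 does not list the calls among the components of rehabilitation, and the SAP does not mention them.

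**Fidelity.** Section 6.7 states: "A researcher will also complete an intervention record log to assess intervention fidelity". Separately, Appendix 1, Stage 4 has a record kept of when and "which rehabilitation classes cancer patient attends recorded".

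**Contamination.** Section 5 frames the Phase 2 question as whether recruited patients are likely to remain in the arm to which they were allocated. Section 6.4 gives controls a "booklet by Bowel Cancer UK, which includes a section on" keeping fit. The SAP repeats the objective but defines no contamination measure or analysis.

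**Adverse events.** Section 10.2 says: "During rehabilitation the cardiac physiotherapist running the exercise class will monitor patients for adverse events". It also provides for a study-long log, and for patients to take health concerns to their cancer nurse. Section 6.7.7 ties serious event reporting to staff becoming aware of the event. The SAP's Adverse Events section reports events by system organ class and preferred term, and its Summary of Study Data section says: "All summary tables will be structured with a column for each treatment in the order (Intervention, Control", plus a total column.

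**The concern.** The trial is unblinded, its primary outcome is physical activity, and the pilot estimate is to inform the sample size of a definitive trial. In that setting, repeated research contact about exercise should be the same in both arms, or at least known in both. Here it is fixed for one arm and open for the other.

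Two reported quantities depend on how information is gathered in each arm. A contamination rate built on exercise advice could count a control who merely read the assigned booklet. It could also miss what matters, which is a control who attended rehabilitation or an equivalent class. A by-arm adverse event table is hard to read as a safety comparison when one arm has a clinician watching for events at each class and the other has no stated enquiry.

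**Working it through.** The plan gives no figure for calls, contamination or adverse event capture, so there is nothing to reproduce. The check counts scheduled contacts and then sets the provisions side by side.

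**Inputs from the documents**
- Expected patients per arm (section 6.2.3): 13 + 13 + 7 = 33.
- Programme length (section 6.4): 8 or 12 weeks by site, with classes once or twice weekly by site.
- Call frequency (section 6.7.4): weekly in the intervention arm, not stated for controls.

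**Scheduled contacts**
- Intervention calls per patient: 8 to 12. In total: 33 × 8 = 264 if every site ran 8 weeks, and 33 × 12 = 396 if every site ran 12.
- Control contacts: unknown. One each would be 33; weekly over the 12 weeks to T1 would be 33 × 12 = 396. The documents therefore allow anything from a large imbalance to none.
- Classes with clinician observation per intervention patient: 8 × 1 = 8 to 12 × 2 = 24. Controls: none.

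**Provisions side by side**

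| Item | Intervention | Control |
|---|---|---|
| Researcher contact during programme | Weekly, telephone | Planned; frequency and form not stated |
| Stated content | Exercise type and duration, education content | Exercise advice, given as an example |
| Active adverse event observation | At classes | None stated |
| Adverse event log, awareness-based serious event reporting | Yes | Yes |
| Emergency visits and admissions asked at each assessment (section 6.9.2) | Yes | Yes |

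The last row shows that a schedule common to both arms already exists. It was written for the economic evaluation, and the SAP leaves service use to the health economics team, so it does not feed the adverse event table as planned.

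**What a call effect would mean if there were one.** This is illustrative; none of its inputs is in the documents. Assume a true effect of 0.3 SD, two-sided 5% and 90% planned power, with n per arm = 2(1.96 + 1.28)² / d². Let the calls add b to the pilot estimate, so that the definitive trial is planned on d = 0.3 + b.

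| b (SD) | Planned n per arm | Power at true 0.3 SD |
|---|---|---|
| 0 | 234 | 90% |
| 0.05 | 172 | 79% |
| 0.10 | 132 | 68% |
| 0.20 | 85 | 50% |

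The table shows only that an added effect of this order would matter for planning. It is not evidence that one exists.

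**The case against.** The strongest reply is that much of what a reader might infer here is not in the text, and most of that reply stands.

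- *The weekly calls collect adverse events in one arm.* No section says so. The contents named for the log are exercise and education. The difference in ascertainment comes from class observation, which exists only where there are classes.
- *The by-arm table will show an excess with rehabilitation.* The documents do not support a direction or a size. Both arms share the log, serious event reporting and the questions on admissions and emergency visits, and NHS records are also available for hospital visits.
- *The calls are a co-intervention that inflates the effect.* This is inference. Intervention patients already have supervised classes, goal setting and action planning, and a logging call may add little. Section 3.2 cites a trial in which telephone counselling raised activity against a contact call. That makes an effect plausible, but counselling is not logging.
- *Contamination cannot be interpreted.* This goes too far. Advice is given only as an example, the booklet could be excluded at coding, and therapy visits, self-reported activity and interviews in both arms give further information. What remains is that no fixed item addresses crossover and no rule excludes the booklet.
- *The calls should be dropped in favour of the class record.* The Stage 4 record covers attendance. It is not stated to hold exercise type, duration or education content, and at some sites the cancer nurse's education is given one-to-one by telephone. Dropping the calls would weaken Objective 9.

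**Conclusion.** The point holds on three limited counts.

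1. Research contact about exercise is weekly in one arm (8 to 12 calls per patient) and unspecified in the other. It may differ between arms, and any effect on activity is an unquantified risk.
2. The one contamination item named for controls does not answer the protocol's own question about staying in the allocated arm, and it overlaps with assigned control material.
3. Class observation (8 to 24 occasions per patient if all are attended) gives the intervention arm an active adverse event source that controls lack, while the SAP sets the arms side by side.

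The call counts rest on the planned 33 per arm and on calls lasting for the whole programme. None of this undermines the recruitment and retention aims. It limits what can be said about contamination, comparative safety and the pilot effect estimate, and the remedy is cheap enough to be worth making.

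**What to change.** 1. **Contamination.** Measure Objective 6 in both arms with the same fixed questions at T1 and T2, added to the both-arm schedule in section 6.9.2: attendance at any cardiac rehabilitation or other supervised exercise class, and receipt of individual activity goals from cardiac rehabilitation staff. State that the assigned booklet does not count. Name these items in the SAP, since it currently leaves service use to the economists.
2. **Adverse events.** Add one identical question at T1 and T2 in both arms. Base the by-arm table on the events it elicits, and list class-observed events separately for the intervention arm. The SAP describes collection in the past tense, so wording there cannot create data. Where the question was not asked, list class-observed events separately and state that ascertainment was unequal. Safety monitoring in class is unchanged.
3. **Research contact.** Keep the weekly fidelity log. Report the number of research contacts by arm, and give any imbalance as a limitation when the pilot effect estimate is used for the definitive trial.

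The cost is protocol and SAP wording and a few extra questions at two visits. The main drawback is recall over about three months. T1 is set at 12 weeks for controls but at the end of an 8- or 12-week programme for intervention patients, so the recall period should be defined and reported by arm.
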